1.10.1.2 Statistical model, hypothesis, and method of analysis

The primary hypothesis tested will be the superiority of canakinumab dose (150mg sc [or 2mg/kg] q4w) relative to placebo with respect to the proportion of responders in the randomized treatment epoch (Epoch 2), where a responder is defined as a patient who has resolution of its index disease flare and does not experience a new flare during the 16 weeks following randomization. The hypothesis within each cohort will be tested at a one-sided 2.5% level.

The statistical hypothesis is that there is no difference in the proportion of patients who respond at Week 16 with the canakinumab dose 150 mg s.c. (or 2mg/kg) q4w versus placebo. Let p_{jk} denote the proportion of responders at Week 16 for treatment group j and cohort k , $k = 1, 2, 3$ for each of the cohorts and $j=0, 1$ where

- 0 corresponds to placebo,
- 1 corresponds to canakinumab 150mg q4w.

The following hypotheses will be tested

- $H_{0k}: p_{1k} - p_{0k} = 0$ versus $H_{A1k}: p_{1k} - p_{0k} > 0$,

In other words:

- H_1 : canakinumab 150 mg q4w is not different to placebo with respect to responder rate at Week 16.

Canakinumab treatment group will be compared to placebo with respect to the proportion of responders at Week 16 using the Fisher's exact test. The proportion of responders, as well as the odds ratio and risk difference with corresponding 95% confidence interval will be presented. The 95% confidence interval for the proportions will be calculated using exact (Clopper – Pearson) method.

1.10.1.3 Handling of missing values/censoring/discontinuations

Patients needing dose escalation in the canakinumab arms, or who escape from placebo to canakinumab in the randomized treatment epoch (Epoch 2), or discontinued from the study due to any reason prior to evaluating the primary endpoint will be considered as non-responders in epoch 2.

1.10.1.4 Supportive analyses

The primary analysis in the randomized treatment epoch will be repeated where definition of the resolution of the index flare and new flare definition will be derived from the centralized SAA values. Resolution of the index flare (initial flare at the time of the randomization) is defined at the Day 15 visit as:

- PGA < 2, and SAA within normal range (≤ 10 mg/L) or reduction of $\geq 70\%$ from baseline

Absence of new flares over the first 16 weeks, where new flare is defined from the time of the resolution of the index flare as:

- PGA ≥ 2 , and SAA ≥ 30 mg/l

If SAA value is missing for the response assessment at scheduled visit then no imputation will be applied and response will be missing.

1.10.1.5 Sensitivity analyses

The primary analysis in the randomized treatment epoch will be repeated on the Full Analysis Set where patients receiving a single add-on injection before Day 15 will be excluded. This implies that the following patients will be excluded:

- patients receiving add-on injection based on criterion from Day 8 to Day 14(persistent PGA ≥ 2 , or CRP persistent > 10 mg/L with less than 40% reduction from baseline from Day 8 to Day 14),
- patients receiving a single add-on injection despite they don't fulfill criterion for add-on injection from Day 8 to Day 14.

A second sensitivity analysis will be performed on the Full Analysis Set where patients receiving a single add-on injection despite they don't fulfill criterion for add-on injection from Day 8 to Day 14 will be excluded.

A third sensitivity analysis will be performed where the primary analysis in the randomized treatment epoch will be repeated on Full Analysis Set where patients receiving a single add-on

injection before Day 15 will be considered as responders except if new flare occurs from Day 15 onward in Epoch 2.

In addition, two more sensitivity analysis will be performed where the primary efficacy analysis on week 16 in the randomized treatment epoch will be repeated on Full Analysis Set

- Where only local values will be used and if missing local CRP values at visit 102 then no resolution of the index flare will be considered.
- Where only central values will be used and if missing central CRP values at visit 102 then no resolution of the index flare will be considered.

1.10.2 Analysis of secondary variables

Secondary efficacy variables will be analyzed separately for each independent cohort (TRAPS, HIDS, crFMF).

The secondary efficacy objectives will be evaluated by assessing the efficacy of canakinumab (q4w in the randomized treatment epoch, and q8w in the randomized withdrawal epoch) as compared to placebo and will be analyzed by cohort. All secondary efficacy objectives will be included in the closed testing procedure.

- to evaluate the percentage of patients who achieve a PGA < 2 at Week 16
- to evaluate the percentage of patients with the serologic remission at Week 16 (defined as C-reactive protein [CRP] ≤ 10 mg/L)
- to evaluate the percentage of patients with normalized Serum Amyloid A (SAA) level at Week 16 (defined as SAA ≤ 10 mg/L)
- to evaluate the percentage of canakinumab responders in Epoch 2 who maintain clinically meaningful response (absence of new flares) when switched to a canakinumab every 8 weeks regimen compared to placebo (Epoch 3).

1.10.2.1 Testing strategy

The following hypotheses will be included in the closed testing procedure, and type-I-errors will be set such that a family-wise type-I-error rate of 2.5% is kept (one sided tests)

- Primary objective: H_1 .

Secondary objectives:

- H_2 : Canakinumab 150mg q4w is not different to placebo with respect to the percentage of patients with PGA < 2 at Week 16.
- H_3 : Canakinumab 150mg q4w is not different to placebo with respect the percentage of patients with CRP ≤ 10 mg/L at Week 16.
- H_4 : Canakinumab 150mg q4w is not different to placebo with respect the percentage of patients with SAA ≤ 10 mg/L at Week 16.
- H_5 : Canakinumab 150mg q8w is not different to placebo with respect to the percentage of responders (absence of new flares) at Week 40.

If the primary objective is achieved, all secondary endpoints in the randomized treatment epoch (Epoch 2) will be assessed. If all secondary objectives are achieved in the randomized treatment epoch (Epoch 2), then the secondary objective in the randomized withdrawal epoch will be tested. The 95% confidence interval for the proportions will be calculated using exact (Clopper-Pearson) method.

Physician's global assessment of disease activity (PGA)

PGA is based on a 5-point scale for disease associated signs and symptoms:

0 (=none/no), 1 (=minimal), 2 (=mild), 3 (=moderate), and 4 (severe).

Frequency tables will be provided by analysis visit and randomized treatment groups for each cohort. Between-treatment differences for the proportion of patients with $\text{PGA} < 2$ at Week 16 will be analyzed using a logistic regression model with treatment group, and baseline PGA as explanatory variables for each cohort. All randomized patients at start of Epoch 2 will be considered for this analysis. Patients needing dose escalation in the canakinumab arms, or who escape from placebo arms to canakinumab in the randomized treatment epoch (Epoch 2), or discontinued from the study due to any reason prior evaluating the endpoint at week 16, will be considered as having $\text{PGA} \geq 2$. If the logistic regression model has difficulty converging due low or high response rates, then Firth's method will be used in the logistic regression model. If the convergence issue is still not resolved then Canakinumab treatment group will be compared to placebo with respect to the proportion of patients with $\text{PGA} < 2$ at Week 16 will be analyzed using the Fisher's exact test.

Serological remission

Serological remission is defined as $\text{CRP} \leq 10\text{mg/L}$. Between-treatment differences for the proportion of patients with $\text{CRP} \leq 10\text{mg/L}$ at Week 16 will be analyzed using a logistic regression model with treatment group, and baseline CRP values as explanatory variables for each cohort. All randomized patients at Epoch 2 will be considered for this analysis. Patients needing dose escalation in the canakinumab arms, or who crossed-over from placebo arms to canakinumab in the randomized treatment epoch (Epoch 2), or discontinued from the study due to any reason prior evaluating the endpoint at week 16, will be considered as having $\text{CRP} > 10\text{mg/L}$. If the logistic regression model has difficulty converging due low or high response rates, then Firth's method will be used in the logistic regression model. If the convergence issue is still not resolved then the canakinumab treatment group will be compared to placebo with respect to the proportion of patients with $\text{CRP} \leq 10\text{mg/L}$ at Week 16 will be analyzed using the Fisher's exact test.

Normalization of SAA

Normalization of SAA is defined as $\text{SAA} \leq 10\text{mg/L}$. Between-treatment differences for the proportion of patients with $\text{SAA} \leq 10\text{mg/L}$ at Week 16 will be analyzed using a logistic regression model with treatment group, and baseline SAA values as effect for each cohort. All randomized patients at Epoch 2 will be considered for this analysis. Patients needing dose escalation in the canakinumab arms, or who crossed-over from placebo arms to canakinumab

in the randomized treatment epoch (Epoch 2), or discontinued from the study due to any reason prior evaluating the endpoint at week 16, will be considered as having SAA > 10mg/L. If the logistic regression model has difficulty converging due low or high response rates, then Firth's method will be used in the logistic regression model. If the convergence issue is still not resolved then the Canakinumab treatment group will be compared to placebo with respect to the proportion of patients with SAA ≤ 10mg/L at Week 16 will be analyzed using the Fisher's exact test.

Maintenance of clinically meaningful response

Responder in the Randomized withdrawal epoch (epoch 3) is defined as no flare between week 16 and week 40. The canakinumab 150mg q8w treatment group will be compared to placebo with respect to the proportion of responders at Week 40 using the Fisher's exact test. Only canakinumab responders in Epoch 2 and re-randomized at week 16 will be considered in the analysis. The proportion of responders, as well as the odds ratio (if estimable) and risk difference with corresponding 97.5% confidence interval will be presented. Canakinumab responders at end of epoch 2 needing dose escalation in the canakinumab arm, or who crossed-over from placebo arm to canakinumab in Epoch 3, or discontinued from the study due to any reason in epoch 3 will be considered as non-responders in epoch 3.

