3.1.3 Randomized withdrawal epoch (Epoch 3)

3.1.3.1 Re-randomization

All patients randomized to placebo at baseline and completing the randomized treatment epoch (Epoch 2) without any re-flare will be considered placebo-responders. To avoid exposure to canakinumab which may not be justified in light of the clinical status, these patients will be withdrawn from the study treatment.

Patients who initiated blinded escape or entered the open-label treatment arm in the randomized treatment epoch (Epoch 2), non-randomized cohort patients and roll-over TRAPS patients will not be re-randomized and will enter the open-label treatment arm in Epoch 3; for patient management details refer to [Section 3.1.3.2](#).

All patients randomized to canakinumab 150 mg (or 2 mg/kg for patients weighing ≤ 40 kg) q4w at baseline and completing the randomized treatment epoch (Epoch 2) who did not require blinded escape or to enter the open-label treatment arm will be re-randomized in a ratio of 1:1 to:

- Canakinumab 150 mg (or 2 mg/kg for patients weighing ≤ 40 kg) q8w
- Placebo

Re-randomized patients will receive the first s.c. injection on Day 113 and will return to the site every 8 weeks to receive additional injections of investigational treatment for 24 weeks.

Visits to assess efficacy and safety are scheduled at 8 weeks intervals during the randomized withdrawal epoch (Epoch 3). Patients might receive an up-titration if they re-flare at unscheduled visits (see [Section 3.1.3.2](#)).

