The study population will consist of male and female patients >28 days and confirmed TRAPS (cohort 1), HIDS (cohort 2), or crFMF (cohort 3).

It is aimed to randomize a total of 180 patients (60 per cohort, 30 per treatment arm) in approximately >20 centers worldwide. Since a 20% screening failure rate is expected, it is estimated that approximately 225 patients have to be screened.

The following patient populations will be screened at Day 1 and directly entered into the open-label treatment arm of the randomized withdrawal epoch (Epoch 3) at Day 113:

- TRAPS patients previously participating in clinical study CACZ885D2203 or the subsequent MPP treatment plan CACZ885D2207M (at most 19 patients).

In addition, the following patient populations will be screened and will enter into the open-label treatment arm of the Epoch 2 at Day 1:

- Male and female patients >28 days but <2 years old with bodyweight ≥ 3.75 kg
- Approximately 5 Japanese crFMF patients with non-exon 10 mutations otherwise fulfilling all the mandatory inclusion and exclusion criteria.

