5.5.13 Study completion and post-study treatment

A patient who completes the baseline visit, is randomized to study drug, continues to participate in all required study visits post randomization up to Day 113 and completes all required assessments is considered a study completer. Site personnel will complete the randomized treatment epoch completion form recording the date the patient last took study medication and whether the patient completed or discontinued from the study.

Enrollment in the screening portion of the study will be closely monitored when the 50th patient per cohort has been randomized. Patients still within the screening portion of the study will terminate their participation after the 60th, and last, patient per cohort has been randomized.

The investigator must provide follow-up medical care for all patients who are prematurely withdrawn from the study, or must refer them for appropriate ongoing care. This care does not require any special treatment but it is recommended not to initiate any live vaccination or biologic treatment until 3 months after the last dose of study treatment.

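### H5 (q8w versus placebo, Week 40): Fisher's exact test is valid but uses only about 0.6% to 1.5% of its one-sided 2.5% at 8 to 15 patients per arm; Boschloo's exact test also stays within 2.5% and never has less power

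*SAP*

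**What the plan says.** SAP 1.10.2.1 (Maintenance of clinically meaningful response) sets the H5 test: the q8w group "will be compared to placebo with respect to the proportion of responders at Week 40 using the" Fisher exact test. Protocol 9.5.1 and the data-analysis part of the protocol summary name the same test. The SAP limits the population: "Only canakinumab responders in Epoch 2 and re-randomized at week 16 will be considered in the analysis". On the level, SAP 1.10.2.1 states that "type-I-errors will be set such that a family-wise type-I-error rate of 2.5% is kept (one sided tests"; H5 comes last and is tested only if H1 to H4 all succeed. SAP 1.10.2 has each disease cohort analysed on its own.

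The size of the comparison follows from the protocol. Section 4 gives the target: "It is aimed to randomize a total of 180 patients (60 per cohort, 30 per treatment arm". Section 5.5.13 closes each cohort: patients still in screening "will terminate their participation after the 60th, and last, patient per cohort has been randomized". Section 3.1.3.1 says that canakinumab patients who "did not require blinded escape or to enter the open-label treatment arm will be re-randomized in a ratio of 1:1 to" q8w or placebo. Roll-over TRAPS patients and the non-randomized groups go to open-label treatment and add nothing to H5.

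**The concern.** Fisher's test conditions on the total number of responders. In small tables its attainable p-values are widely spaced, so the real error rate can lie well below the nominal level. H5 is the smallest comparison in the confirmatory sequence and the only one there that addresses the trial's second purpose, whether efficacy holds at the 8-week interval. Type I error that is allotted but not used costs power, in rare diseases where more patients are hard to find.

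Boschloo's test takes the Fisher p-value as its statistic and raises the cut-off as far as possible while the maximum error over all common response rates stays at or below 2.5%. The cut-off is never below 0.025, so its rejection region contains Fisher's.

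**Working it through.** **Plan's own figure.** The documents show no power or expected rates for H5. The visible sample-size text concerns only the Week 16 primary comparison, and part of it is blacked out in the public version. So there is no H5 figure to reproduce.

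**Arm size.** At most 30 canakinumab patients per cohort (60 randomized 1:1), re-randomized 1:1: 30/2 = 15 per arm if all qualify, give or take one. Protocol 1.1 reports pilot response rates of at least 85%, on other endpoints and regimens. If 85% qualified (an assumption), 0.85 × 30 = 25.5, that is 13/12 or 13/13. Epoch 3 discontinuations count as non-responders, so the arms do not shrink.

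**Method.** Let x of n1 q8w patients and y of n2 placebo patients be flare-free, with m = x + y.
- One-sided Fisher p = Σ(k ≥ x) C(n1,k)·C(n2,m−k) / C(n1+n2,m). Fisher rejects if p ≤ 0.025.
- Size of a rejection region R = max over θ of Σ(x,y in R) Bin(x; n1,θ)·Bin(y; n2,θ).
- Boschloo's region = {p ≤ c}, with c the largest cut-off for which the size is ≤ 0.025.
- Power = Σ(x,y in R) Bin(x; n1,p1)·Bin(y; n2,p0).

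All 2×2 tables were enumerated exactly, with θ on a fine grid. The flare-free rates are assumptions.

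| Arms | Fisher max. size | Boschloo max. size | Power, 0.7 vs 0.3 (gain) | Power, 0.8 vs 0.2 (gain) |
|---|---|---|---|---|
| 15/15 | 0.88% | 2.16% | 43.4% → 59.0% (+15.6) | 87.2% → 93.9% (+6.7) |
| 13/13 | 1.45% | 2.43% | 46.1% → 49.4% (+3.3) | 86.9% → 88.3% (+1.4) |
| 13/12 | 1.01% | 2.49% | 34.9% → 51.5% (+16.6) | 78.5% → 89.2% (+10.7) |
| 11/10 | 1.37% | 2.36% | 36.4% → 39.1% (+2.7) | 77.0% → 78.8% (+1.7) |
| 10/10 | 0.64% | 2.11% | 24.3% → 41.8% (+17.5) | 63.5% → 80.5% (+17.0) |
| 8/8 | 1.06% | 1.39% | 24.6% → 26.2% (+1.6) | 59.8% → 61.4% (+1.5) |

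Over 8 to 15 per arm, Fisher's maximum size lies between 0.64% (10/10) and 1.45% (13/13). The unused share of the level is 1 − 0.88/2.5 = 65% at 15/15, but 1 − 1.45/2.5 = 42% at 13/13. Boschloo's region contained Fisher's at every size enumerated.

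**One table.** At 15/15 with 10 versus 4 flare-free (m = 14), Fisher p = (3003·1365 + 1365·455 + 455·105 + 105·15 + 15·1) / C(30,14) = 4,769,535 / 145,422,675 = 0.033. Fisher does not reject. Boschloo's cut-off on this p-value at 15/15 is 0.0498, so Boschloo does.

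**H1 for comparison.** At 30/30, Fisher's size is 1.37% and power for 0.7 vs 0.3 goes from 83.8% to 88.4%, a smaller gain from a higher start.

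**The case against.** The best defence is that nothing is broken. Fisher's test is exact, familiar, named consistently in both documents, and keeps the family-wise level. The same test serves H1. A reader might infer from the low attained size that the plan miscontrols its error; it does not, since conservatism errs on the safe side. This stands: the point is about efficiency only.

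The size of the benefit is also open. A reader might infer that Fisher's true level is always 1% or less, or that more than half of the level is always lost. Neither holds: 13/13 gives 1.45% and 11/10 gives 1.37%, with 42% and 45% unused. Nor can a single range of power gain be quoted for the design. For 0.7 vs 0.3, one patient separates a gain of 16.6 points (13/12) from 3.3 points (13/13), and the final arm sizes cannot be known in advance. This also stands, so each gain has to be read with its arm sizes and rates.

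Finally, Boschloo's test does not solve the small sample. At 0.7 vs 0.3 it reaches 59% at 15/15, and H5 is reached only after four earlier successes. A log-rank comparison of time to first flare in the same patients is already planned (protocol 9.5.2, SAP 1.10.5), but as exploratory, so it does not replace the confirmatory test. None of this argues for keeping the less powerful of two valid tests.

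**Conclusion.** The point holds as a cheap improvement, not as an error in the plan. With about 15 patients per arm at most, Fisher's test for H5 works at a true one-sided level of about 0.6% to 1.5%. Boschloo's test stays at or below 2.5%; it does not use the level in full either (1.39% at 8/8, 2.16% at 15/15). Its power is never lower.

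Under assumed flare-free rates the gain runs from under 2 points (8/8 at 0.7 vs 0.3; 13/13 at 0.8 vs 0.2) to 15 points or more (15/15, 13/12 and 10/10 at 0.7 vs 0.3). The size figures and the ordering of the two tests rest only on the arm sizes. The power figures also rest on rates that the documents do not supply.

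**What to change.** Amend protocol 9.5.1, the protocol summary and SAP 1.10.2.1 so that H5 is tested with the one-sided Boschloo exact unconditional test at 2.5%, and report Fisher's p-value as supportive. Do this before any unblinded Epoch 3 data are seen, and preferably before the Week 16 unblinding, so that the choice cannot be linked to results. H1 can stay as planned.

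Costs: because the protocol names Fisher's test, protocol 11.1 requires a written amendment; SAP wording alone is not enough. The test is less familiar to readers. The planned intervals for the odds ratio and risk difference may not agree exactly with the Boschloo decision, so the SAP should say that the test decides. Patients, visits and treatment are unaffected.

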Safety data for the subgroup of canakinumab naïve Japanese crFMF patients with non-exon 10 mutations, and patients >28 days but <2 years old, collected in Epoch 2, 3 and 4 will separately be reported from the other patients who will be screened and randomized in Epoch 2. Summary statistics for continuous variables will include N, mean, standard deviation, minimum, lower quartile, median, upper quartile, maximum. Summary statistics for discrete variables will be presented in contingency tables and will include absolute and relative frequencies.

If not otherwise specified, p-values will be presented as two-sided p-values and two-sided confidence intervals will be displayed.

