- a. A screening epoch to assess patients' eligibility of up to 12 weeks duration (Epoch 1)
- b. An open-label epoch of 16 weeks (Epoch 2)
- c. An open-label epoch of 24 weeks (Epoch 3)

- d. An open-label treatment epoch of 72 weeks to collect long-term safety data for canakinumab (Epoch 4)

All data will be analyzed separately for each independent cohort (TRAPS, HIDS, crFMF).

The purpose of the study is to provide evidence supporting answers to following questions. The data will be analyzed by Epoch:

1. Whether canakinumab at a starting dose of 150mg s.c. (or 2mg/kg for patients ≤ 40 kg) administered every 4 weeks is able to induce and maintain a clinically meaningful reduction of disease activity defined as resolution of the index flare at Day 15 and no new disease flares over 16 weeks of treatment in a greater proportion of patients with TRAPS, HIDS, or crFMF compared to placebo (Data from Epoch 2)
2. Whether, in patients responding to the initial dosing regimen of every 4 weeks, canakinumab will maintain its clinical efficacy if administered at a reduced dosing interval of 150mg s.c. (or 2mg/kg for patients ≤ 40 kg) every 8 weeks. (Data from epoch 3 and 4)

Safety data for the subgroup of patients coming from ACZ885D2203 and/or the subsequent Multiple Patient Program (MPP) treatment plan CACZ885D2207M collected in Epoch 3 and 4 will separately be reported from the other patients who will be screened and randomized in Epoch 2.

Safety data for the subgroup of canakinumab naïve Japanese crFMF patients with non-exon 10 mutations, and patients >28 days but <2 years old, collected in Epoch 2, 3 and 4 will separately be reported from the other patients who will be screened and randomized in Epoch 2.

Summary statistics for continuous variables will include N, mean, standard deviation, minimum, lower quartile, median, upper quartile, maximum, and number of patients with non-missing data (n). Summary statistics for discrete variables will be presented in contingency tables and will include absolute and relative frequencies.

If not otherwise specified, p-values will be presented as two-sided p-values and two-sided confidence intervals will be displayed.

All listings will be presented by cohort and treatment sequence.

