Rescue medications are not collected visit wise in the study and are collected in summary page as part of concomitant medications. Rescue medications will be mapped to visits. Rescue medications shall be assigned to visit based on start and end date of the medication and corresponding visit date. For example, if visit date for visit 103 lies between start and end date of "VALISONE-G" corticosteroid then dose level of this concomitant medication will be assigned to visit 103. If there are more than one dose that are assigned to same visit then these

doses shall be added after converting the units to mg/kg/day. If there are no records of rescue medication for any visit then it shall be considered as 0 mg/kg/day dose.

Blinded escape

The number and percentage of patients who require blinded escape from Days 8 to 28 will be summarized by cohort and randomized treatment group.

Auto-Inflammatory Disease Activity Index (AIDAI)

Symptoms evaluated in the AIDAI diary will be summarized with each cohort and epoch (2 and 3) and by treatment group (as defined in [section 1.3](#)) for monthly score as sum of scores over a month. Spaghetti plot will be provided by subject and cohort and initial randomized treatment.

Time to first new flare in the randomized withdrawal epoch (Epoch 3)

Time to first new flare in Epoch 3 will be analyzed for patients re-randomized at the start of epoch 3. The two treatment groups (150mg q8w and placebo) will be compared using a one-sided log-rank test at the 2.5% significance level. The hazard ratio and its associated 95% two-sided confidence intervals will be estimated. Kaplan-Meier estimates of the probability to experience a flare event will be calculated from the start of the randomized withdrawal epoch. 95% confidence intervals using Greenwood's formula will be provided.

Patients who discontinued the study in epoch 3, or having an up-titration or escape from placebo group to canakinumab arm will be counted as having a flare in epoch 3. In this case the date of the premature subject withdrawal (PSW) visit, or resp. time of up-titration or escape is considered as the end date for the calculation of time to flare.

SF-12 Health Survey (SF-12)

SF-12 scores will be summarized (descriptively) by epoch (2 and 3), analysis visit, initial randomized treatment and treatment sequence (as defined in [section 1.3](#)) within each cohort. Only patients ≥ 18 years of age at baseline will be part of the analyses.

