1.15 Determination of sample size

The primary efficacy objective in the randomized treatment epoch and for the overall study is to compare canakinumab treatment to placebo with respect to the proportion of responders at Week 16 using the Fisher's exact test. The proportion of responders, as well as the odds ratio (if estimable) and risk difference with corresponding 97.5% confidence interval will be presented.

Since a 20% screening failure rate is expected, it is estimated that approximately [REDACTED] patients have to be screened.

Nquery Advisor® software version 7.0 was used.

2 Clinical Study Report - Appendix 16.1.9 Documentation of statistical methods

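### The 97.5% intervals for the Epoch 3 withdrawal comparison (H5) do not match the one-sided 2.5% test, and SAP 1.15 and the protocol contradict the 95% that SAP 1.10.1.2 sets for the primary analysis

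*SAP*

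**What the plan says.** **Test level.** For the primary analysis, SAP 1.10.1.2 says: "The hypothesis within each cohort will be tested at a one-sided 2.5% level". SAP 1.10.2.1 puts H1 to H5 in one hierarchy with a one-sided family-wise error rate of 2.5%. H1 and H5 are each decided by Fisher's exact test.

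**Default for intervals.** The introduction to protocol section 9 says that, unless otherwise specified, "p-values will be presented as two-sided p-values and two-sided confidence intervals will be displayed". SAP 1.1 repeats the rule.

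**Interval level for the odds ratio and risk difference.**

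| Comparison | Place | Level |
|---|---|---|
| Primary (H1) | SAP 1.10.1.2 | 95% |
| Primary (H1) | SAP 1.15 | 97.5% |
| Primary (H1) | Protocol summary, 9.4.2, 9.7 | 97.5% |
| Epoch 3 (H5) | SAP 1.10.2.1 | 97.5% |
| Epoch 3 (H5) | Protocol 9.5.1 | 97.5% |

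The SAP wording for H5 is "risk difference with corresponding 97.5% confidence interval will be presented". For the primary analysis, SAP 1.10.1.2 has "risk difference with corresponding 95% confidence interval" and SAP 1.15 has "risk difference with corresponding 97.5% confidence interval". None of the 97.5% statements says whether the interval is one-sided or two-sided.

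**The same Epoch 3 arms, time to first flare (exploratory).** SAP 1.10.5 and protocol 9.5.2 specify a one-sided log-rank test at 2.5%, and then: "The hazard ratio and its associated 95% two-sided confidence intervals will be estimated".

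**The concern.** An interval reported beside a test should normally use the same tail probability, so that the reader can see the test result in it. A one-sided 2.5% test goes with a two-sided 95% interval. The plan follows that pairing for time to flare in Epoch 3 and for the primary analysis in SAP 1.10.1.2, but not for H5, where both documents give 97.5% and no passage gives 95%. A programmer following the SAP would therefore produce 97.5% intervals for H5.

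Three things are at stake, all in reporting:

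- The H5 intervals would be wider than the stated test implies.
- They would sit at a different level from the primary and time-to-flare intervals, and from the 95% Clopper-Pearson intervals that SAP 1.10.2.1 gives for the single proportions.
- A significant H5 result could appear with an odds-ratio interval that includes 1.

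For the primary contrasts, the SAP gives two levels for the same quantity. That conflict cannot be settled by letting the SAP override the protocol.

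**Working it through.** **Step 1. Match the level to the test.** A two-sided interval at level L leaves (1 − L)/2 in each tail; a one-sided bound at level L leaves 1 − L.

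| Interval | Tail | z | Matches one-sided 2.5%? |
|---|---|---|---|
| Two-sided 97.5% | (1 − 0.975)/2 = 0.0125 | 2.241 | No |
| Two-sided 95% | (1 − 0.95)/2 = 0.025 | 1.960 | Yes |
| One-sided 97.5% bound | 1 − 0.975 = 0.025 | 1.960 | Yes |

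The width ratio of the first to the second is 2.241/1.960 = 1.144, about 14% wider on the normal scale. The third row would match, but the default requires an exception to be specified and none is.

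**Step 2. Size of the H5 comparison.** The visible text gives no number for H5, and the sample-size sections are partly blacked out. Protocol section 4 plans 30 patients per arm in each cohort, and protocol 3.1.3.1 re-randomizes eligible canakinumab patients 1:1. If every one were re-randomized, that is 30/2 = 15 per arm. I assume 8 to 15 per arm.

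**Step 3. One example: 11/15 against 4/15 without a flare.** One-sided Fisher p = 0.0134, significant at 2.5%.

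- Risk difference: 11/15 − 4/15 = 7/15 = 0.467. Standard error: √(2 × (11/15)(4/15)/15) = 0.1615.
- Wald interval at 95%: 0.467 ± 1.960 × 0.1615 = 0.150 to 0.783.
- Wald interval at 97.5%: 0.467 ± 2.241 × 0.1615 = 0.105 to 0.829.
- Odds ratio: (11 × 11)/(4 × 4) = 7.56. Standard error of its log: √(1/11 + 1/4 + 1/4 + 1/11) = 0.826.
- Wald lower limit: exp(ln 7.56 − 1.960 × 0.826) = 1.50 at 95%; with 2.241 in place of 1.960, 1.19 at 97.5%.
- Exact conditional lower limit (the odds ratio at which the upper-tail conditional probability equals the tail): 1.20 at 95%, 0.98 at 97.5%.

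The exact conditional odds ratio is the one method here for which the 97.5% interval includes no effect although the test is significant.

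**Step 4. All tables.** I listed every 2×2 table with one-sided Fisher p ≤ 0.025 in favour of canakinumab and counted those whose two-sided 97.5% interval includes no effect.

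| Per arm | Exact conditional OR | Wald OR (no zero cell) | Wald RD | Newcombe RD |
|---|---|---|---|---|
| 8 | 4 of 10 | 0 of 3 | 0 of 10 | 0 of 10 |
| 10 | 2 of 17 | 0 of 6 | 0 of 17 | 0 of 17 |
| 12 | 7 of 30 | 0 of 15 | 0 of 30 | 0 of 30 |
| 15 | 7 of 51 | 2 of 30 | 0 of 51 | 0 of 51 |

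At two-sided 95% the count is 0 for all four methods at every size. These are counts of tables, not probabilities. The two odds-ratio columns have different denominators and should not be compared with each other.

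**The case against.** **A one-sided 97.5% bound may have been meant.** It is the complement of one-sided 2.5%, protocol 9.4.2 gives both figures in the same section, and the time-to-flare interval is labelled two-sided where these are not. Such a bound would match the test. This stands as a possible intention, but the default in both documents makes an unlabelled interval two-sided, so the text needs correcting on either reading.

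**Nothing inferential changes.** This stands. Fisher's test decides, no rule reads H5 from the interval, and a two-sided 97.5% interval is valid, only wider.

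**The visible disagreement depends on an unnamed method.** This also stands. Neither risk-difference method shows it, and the Wald odds ratio shows it only at 15 per arm. The plan presents the H5 odds ratio only where it can be estimated. If that drops tables with a zero cell, the exact conditional counts become 2 of 3, 0 of 6, 5 of 15 and 5 of 30, so at 10 per arm the disagreement disappears. This changes the illustration, not the mismatch of levels.

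**SAP 1.15 only restates the analysis.** SAP 1.10.1.2 is indeed the operative section for the primary analysis, and 1.15 looks like text left unaligned rather than a second analysis. H5 has no such correct passage to fall back on.

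**Conclusion.** The concern holds. Under the documents' own two-sided default, the H5 odds ratio and risk difference are given intervals with 1.25% per tail beside a 2.5% one-sided test, about 14% too wide on the normal scale. For the primary contrasts, SAP 1.10.1.2 (95%) is contradicted by SAP 1.15 and by three places in the protocol (97.5%). The effect is confined to reporting. Whether a significant H5 result would be shown with an interval including no effect depends on the interval method, which is not named, and on the number per arm, assumed here to be 8 to 15. It should be corrected because H5 is a confirmatory hypothesis in the hierarchy and the Week 40 report may support health authority interactions.

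**What to change.** State two-sided 95% for the odds ratio and risk difference in SAP 1.10.2.1 (H5) and SAP 1.15, and align the protocol summary and protocol 9.4.2, 9.5.1 and 9.7. This agrees with SAP 1.10.1.2 and with the time-to-flare analysis, and it removes the disagreement for all four interval methods examined. Labelling 97.5% as a one-sided bound would also match the test, but would leave H5 reported differently from the primary analysis in SAP 1.10.1.2.

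It is advisable, though not essential, to name the interval methods. An exact conditional odds-ratio interval agrees with Fisher's test; its price is width (lower limit 1.20 against 1.50 for Wald at 95% in the example). Make the change before Week 40 results are seen, so that the level cannot appear to have been chosen from the data. The cost is wording only: sample size, power, type I error and testing order do not change.
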